12.5 Handling of Missing Data

All data obtained in evaluable subjects/eyes will be included in the analysis. No imputation for missing values will be carried out.

12.6 Safety Analyses

The safety endpoints are:

- AEs
- Biomicroscopy findings
- Device deficiencies

There are no safety hypotheses planned in this study. The focus of the safety analysis will be a comprehensive descriptive assessment of occurrence of adverse events as well as the other listed parameters.

All AEs occurring from the time a subject signs informed consent to study exit will be accounted for in the reporting. Safety analyses will be conducted using the safety analysis set on a treatment-emergent basis. Descriptive summaries (counts and percentages) for ocular and nonocular AEs will be presented by Medical Dictionary for Regulatory Activities Preferred Terms. AEs leading to study discontinuation, significant non-serious AEs, and SAEs will be identified. Individual subject listings will be provided, as necessary.

Individual subject listings will be provided for AEs that occur after signing informed consent but prior to exposure to IP.

Each biomicroscopy parameter will be tabulated by its grade. For each biomicroscopy parameter, counts and percentages of eyes that experience an increase of ≥ 2 grades from baseline (last assessment prior to study lens exposure for each period) to any subsequent visit within the same period will be presented. A supportive listing will be generated which will include all biomicroscopy data from all visits within the same period for those eyes experiencing the increase.

Two listings for device deficiencies, prior to exposure of study contact lenses and treatment-emergent, will be provided. Additionally, each device deficiency category will be tabulated.

No inferential testing will be done for safety analysis.

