7 INVESTIGATIONAL PLAN

7.1 Study Design

[figure not shown]
This is a prospective, randomized, [REDACTED] bilateral crossover, controlled, subject-masked, daily wear clinical study to be conducted at a single site. Eligible habitual soft contact lens wearers will be randomized to 1 of the 2 crossover sequences. Subjects will be masked. A designated study staff member will prepare the contact lenses for dispensing.

Subjects will be expected to participate in a pre-screening and attend 3 office visits: Screen/Baseline/Dispense Lens Pair 1, Follow-up Lens Pair 1/Dispense Lens Pair 2, Follow-up Lens Pair 2/Exit. AOHP will be worn for ~14 days and TOTAL30 will be worn for ~28 days. The total expected duration of participation for each subject is approximately 1.5 months. Subjects will be randomized to wear the assigned product sequence in both eyes, either the test TOTAL30 contact lenses as Pair 1, followed by the comparator AOHP contact lenses as Pair 2, or vice versa. All study contact lenses will be prescribed according to subject's prescription and can be optimized per study lens type, however test and comparator lenses should be dispensed within ± 0.25 D of each other.

Subjects will be expected to wear their study contact lens in a daily wear modality for at least 5 days per week 8 hours a day, over a 14 day (AOHP) or 28 day period (TOTAL30). AOSEPT PLUS with HydraGlyde Cleaning & Disinfecting Solution will be used for daily cleaning and disinfection.

On the day of Visits 2 and 3, subjects will be asked to wear the study lenses at least 6 hours and prior to their study visit. Follow-up visit time to be within ± 2 hours of baseline visit time.

[REDACTED]
[REDACTED]

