8.2 Exclusion Criteria

Subjects fulfilling **any** of the following criteria are not eligible for participation in this study.

1. Any anterior segment infection, inflammation, or abnormality or disease (including systemic) that contraindicates contact lens wear, as determined by the investigator.
2. Any use of systemic or ocular medications for which contact lens wear could be contraindicated, as determined by the investigator.
3. History of refractive surgery or plan to have refractive surgery during the study or irregular cornea in either eye.

4. Ocular or intraocular surgery (excluding placement of punctal plugs) within the previous 12 months or planned during the study.
5. Biomicroscopy findings at screening that are moderate (Grade 3) or higher and/or corneal vascularization that is mild (Grade 2) or higher; presence of corneal infiltrates.
6. Current or history of pathologically dry eye in either eye that, in the opinion of the investigator, would preclude contact lens wear.
7. Current or history of herpetic keratitis in either eye.
8. Eye injury in either eye within twelve weeks immediately prior to enrollment for this trial.

10. Any use of topical ocular medications and artificial tear or rewetting drops that would require instillation during the study.
11. The investigator, his/her staff, family members of the investigator, family members of the investigator's staff, or individuals living in the households of the aforementioned persons may not participate in the study.
12. Participation of the subject in a clinical trial within the previous 14 days or currently enrolled in any clinical trial.
13. Monovision wear during the study.
14. Habitual AOHP contact lens wearers (in the past 3 months)
15. Currently pregnant or breast-feeding.

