10 STUDY PROCEDURES AND ASSESSMENTS

Visit #	Visit Type	Visit Day	Visit Window
Visit 1	Screen/Baseline/Dispense Pair 1	Day 1	N/A
Visit 2	Follow-up Pair 1 (Dispense Pair 2) AOHP: Day 14 TOTAL30: Day 28	Day 14 Day 28	Days 11-21 Days 25-35
Visit 3	Follow-up Pair 2/Exit AOHP: Day 14 TOTAL30: Day 28	Day 14 Day 28	Days 11-21 Days 25-35

Unscheduled Visits and Early Termination Visits are allowed, if necessary.

Study lenses will be provided to the subjects to take home for daily wear during the course of the trial.

Study randomization will occur at Visit 1 with assigned lenses provided to take home at Visit 1 and Visit 2. Study contact lens fitting will occur at Visit 1 for both study lenses. If a subject cannot be successfully fit (either study lens) according to the study lens fitting guides as determined by the investigator, they will be required to exit from the study.

Lubrication/rewetting drops will not be permitted during this study.

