5.3 Statistical Methods for Safety Analyses

The analysis set for all safety analyses is defined in Section 2.1. Baseline will be defined as the last measurement prior to exposure to study lenses. For biomicroscopy data, baseline will be defined as Visit 1 for pair 1 and Visit 3 for pair 2.

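### The Pair 2 slit-lamp baseline is an on-lens Pair 1 result in the protocol and the exit visit in the SAP; correct the SAP, and show a Visit 1-referenced table beside the period-baseline one

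*Protocol*

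**What the plan says.** Protocol 12.6 tabulates, for each biomicroscopy parameter, the eyes that worsen by 2 or more grades from "baseline (last assessment prior to study lens exposure for each period", up to any later visit in that period. The schedule in Protocol 10 describes Visit 2 as "Follow-up Pair 1 (Dispense Pair 2" and Visit 3 as "Follow-up Pair 2/Exit". Protocol Table 3-1 schedules biomicroscopy at Visits 1, 2 and 3 and at early exit, and only as necessary at unscheduled visits.

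On the day of Visits 2 and 3, Protocol 7.1 says that "subjects will be asked to wear the study lenses at least 6 hours and prior to their study visit". The one grade limit is exclusion criterion 5 in Protocol 8.2, which removes subjects with "Biomicroscopy findings at screening that are moderate (Grade 3) or higher" (a lower limit applies to corneal vascularization). It applies at screening only.

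SAP 5.3 gives a general rule, "Baseline will be defined as the last measurement prior to exposure to study lenses", and then states: "For biomicroscopy data, baseline will be defined as Visit 1 for pair 1 and Visit 3 for pair 2". SAP 5.3.2 plans the 2-grade table and its listing, a summary by visit, and separate listings for infiltrates, for compression or chemosis, and for other findings.

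**The concern.** Two problems sit on the same line of the plan.

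The first is a contradiction. Visit 3 comes after Pair 2 has been worn, so it cannot be the Pair 2 baseline under Protocol 12.6 or under the SAP's own preceding sentence. Programmed as written, the SAP compares the last scheduled Pair 2 examination with itself.

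The second remains after that correction. The Visit 2 examination is the Pair 1 outcome, taken on a day of Pair 1 wear, and it then serves as the starting point for Pair 2. Whatever Pair 1 did to the eye is subtracted from what Pair 2 is seen to do. Pair 1, by contrast, starts from a Visit 1 grade limited by eligibility. At stake is which eyes the 2-grade table and its listing can identify, and whether a lens's incidence means the same thing in the two periods.

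**Working it through.** The documents give no expected rate, sample size calculation or power for this endpoint, so there is no planned figure to reproduce. The check is arithmetic on grades.

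**Inputs.** Biomicroscopy at Visits 1, 2 and 3 (Protocol Table 3-1). Pair 2 dispensed at Visit 2 (Protocol 10). Threshold of 2 grades (Protocol 12.6). 32 planned completers (Protocol 3), so 64 eyes per lens, since each completer wears both lenses in both eyes. Allocation 1:1 (SAP 1.3), so about 32 of those 64 eyes wear a given lens as Pair 2. The top of the grading scale is not visible; Protocol 8.2 shows only that Grade 2 is mild and Grade 3 moderate.

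**Step 1: which eyes are flagged.** An eye is flagged for a pair if follow-up grade minus baseline grade is at least 2.

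| Grades at Visits 1/2/3 | Pair 1 (V2−V1) | Pair 2, Protocol 12.6 (V3−V2) | Pair 2, SAP 5.3 (V3−V3) | Pair 2 against Visit 1 (V3−V1) |
|---|---|---|---|---|
| 0/2/2 | 2, flagged | 0, no | 0, no | 2, flagged |
| 0/1/2 | 1, no | 1, no | 0, no | 2, flagged |
| 2/3/4 | 1, no | 1, no | 0, no | 2, flagged |
| 1/3/4 | 2, flagged | 1, no | 0, no | 3, flagged |
| 0/1/3 | 1, no | 2, flagged | 0, no | 3, flagged |
| 0/2/4 | 2, flagged | 2, flagged | 0, no | 4, flagged |

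The SAP column is zero throughout: at scheduled visits no Pair 2 increase can be counted, in any of the 64 Pair 2 eyes (32 per lens). Under the protocol column, a shared reaction (0/2/2) is counted for Pair 1 only, and a stepwise rise (0/1/2 or 2/3/4) is counted for neither. The 0/1/2 case needs no assumption about the scale; 2/3/4 needs a top grade of at least 4.

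**Step 2: possible size after the SAP is corrected to Visit 2.** Let p be the proportion of eyes that reach 2 grades above their Visit 1 level on each lens. Assume a Pair 1 reaction is still present at Visit 2 and does not worsen by a further 2 grades. A lens's tabulated incidence averages its period 1 rate (p) and its period 2 rate:

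- same eyes react to both lenses: (p + 0)/2
- reactions independent: (p + p(1 − p))/2

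| Assumed p | Same eyes | Independent | Shortfall in 64 eyes |
|---|---|---|---|
| 5% | 0.05/2 = 2.5% | (0.05 + 0.0475)/2 = 4.9% | 1.6 down to 0.08 eyes |
| 10% | 0.10/2 = 5.0% | (0.10 + 0.09)/2 = 9.5% | 3.2 down to 0.3 eyes |

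The shortfall is 64 × (p − tabulated rate): for example 64 × 0.025 = 1.6 and 64 × 0.00125 = 0.08. The rates of 5% and 10% are assumptions. The shortfall is measured against a Visit 1 reference, and the stepwise cases are not included.

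**Step 3: ceiling.** A baseline grade g can be flagged only if top grade − g is at least 2.

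- Top grade 4 (assumed): every eligible Visit 1 grade has room, but a Visit 2 grade of 3 or 4 does not.
- Top grade 3: Grade 2 is blocked at Visit 1 as well, so the contrast between visits is weaker.
- Top grade 5: only Grades 4 and 5 are blocked.

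With a top grade of 4, if 1% to 20% of the 64 Pair 2 eyes stood at Grade 3 or above at Visit 2, then 0.6 to 12.8 eyes could not be flagged. Nothing in the documents narrows that range.

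**The case against.** The strongest reply is that this is what a period baseline is for. The safety analysis is treatment-emergent, and a finding that arose on Pair 1 is charged once, to the lens on which it arose. Referring Pair 2 to Visit 1 would charge one lens with what the other left behind. That stands, and it is why Visit 1 should not replace the period baseline. It does not cover the stepwise eye, which is charged to no lens, or the eye in which the second lens would have produced the same reaction by itself.

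Visit 1 is also not shown to be a lens-free reference. Subjects are habitual soft lens wearers, and the visible text sets no lens-free interval before that visit. This too stands as a limit on the supplementary table.

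Next, other outputs remain: tabulation by grade (Protocol 12.6), the by-visit summary and the separate listings (SAP 5.3.2), and reporting of clinically relevant changes as adverse events (Protocol 11.2). So the findings are not lost. But the grade and by-visit summaries are not described as linking one eye's grades across visits, and the 2-grade listing covers only flagged eyes, within one period. Adverse event reporting rests on the judgment of investigators whom Protocol 11.5 calls unmasked.

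Finally, this is a descriptive feasibility study with no success criterion, so no decision rule hangs on the table. That limits the weight of the point.

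A reader might infer that the lens worn second is made to look safer than its competitor. The documents do not support that: with 1:1 allocation each lens is second in about half the subjects. The wear before the Pair 2 baseline does differ by sequence (about 28 days of TOTAL30 or 14 of AOHP), so the effect need not be equal, but neither its direction nor its size can be derived.

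**Conclusion.** The SAP's Visit 3 baseline for Pair 2 is a plain inconsistency and the larger error: it makes the Pair 2 count zero at scheduled visits by construction. It should be settled first.

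Once it is corrected, a narrower limitation remains. The Pair 2 baseline is an on-lens Pair 1 result with no grade limit. The 2-grade table therefore omits shared reactions for the second lens and stepwise rises altogether, and the two periods of one lens measure different quantities. Under the assumptions in step 2, the loss runs from negligible, if reactions are independent, to half of a lens's events, if the same eyes react to both. The ceiling effect cannot be judged without the grading scale. It would go too far to call the period-baseline table wrong, or to treat change from Visit 1 as the true Pair 2 incidence; neither document sets that target.

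**What to change.** 1. Correct SAP 5.3 so that the biomicroscopy baseline is Visit 1 for Pair 1 and Visit 2 for Pair 2, in agreement with Protocol 12.6.
2. Keep the period-baseline 2-grade table and listing as planned.
3. Add one supplementary table and listing, by lens and sequence, with Visit 1 as the reference for both pairs. A Visit 1/2/3 grade shift table by sequence would serve the same purpose.
4. State in a footnote that the supplementary table may attribute residual Pair 1 findings to Pair 2, and that Visit 1 may itself follow habitual lens wear. Read the descriptive safety summary from both tables.

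The cost is one corrected visit number plus one table and one listing from data already collected. Visits, examinations and study conduct do not change.

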12.7 Sample Size Justification

Given the feasibility nature of this study, sample size calculation is not relevant.

13 DATA HANDLING AND ADMINISTRATIVE REQUIREMENTS

13.1 Subject Confidentiality

The investigator must ensure that the subject's identity is kept confidential throughout the course of the study. In particular, the investigator must keep an enrollment log with confidential identifying information that corresponds to the subject numbers and initials of each study participant. The study sponsor may collect a copy of the enrollment log *without any identifying subject information*.

The study sponsor may share patient-level data collected in this trial with qualified researchers to help facilitate product development or enhancements in research that is not directly related to the study objectives. The Informed Consent explains this to the study subject.

13.2 Completion of Source Documents and Case Report Forms

The nature and location of all source documents will be identified to ensure that original data required to complete the CRFs exist and are accessible for verification by the site monitor, and all discrepancies shall be appropriately documented via the query resolution process. Site monitors are appointed by the study sponsor and are independent of study site staff.

If electronic records are maintained, the method of verification must be determined in advance of starting the study.

At a minimum, source documents include the following information for each subject:

- Subject identification (name, sex, race)
- Documentation of subject eligibility
- Date of informed consent
- Dates of visits
- Documentation that protocol specific procedures were performed
- Results of study parameters, as required by the protocol
- IP accountability records
- Documentation of AEs and other safety parameters (if applicable)

- Records regarding medical histories and the use of concomitant therapies prior to and during the study
- Date of study completion and reason for early discontinuation, if applicable

It is required that the author of an entry in the source documents be identifiable. Direct access to source documentation (medical records) must be allowed for the purpose of verifying that the data recorded on the CRF are consistent with the original source data.

Only designated individuals at the site will complete the CRFs. The CRFs must be completed at regular intervals following the clinical study visit schedule. It is expected that all data reported have corresponding entries in the source documents. The principal investigator is responsible for reviewing and certifying that the CRFs are accurate and complete. The only subject identifiers recorded on the CRFs will be subject number, and subject demographic information.

13.3 Data Review and Clarifications

A review of CRF data to the subject's source data will be completed by the site monitor to ensure completeness and accuracy. After the CRFs have been completed, additional data clarifications and/or additions may be needed as a result of the data cleaning process. Data clarifications are documented and are part of each subject's CRF.

13.4 Sponsor and Monitoring Responsibilities

The study sponsor will select principal investigators that are qualified by education, training, and experience to assume responsibility for the proper conduct of this clinical trial.

The study sponsor is financially funding this clinical trial and will compensate the investigator and/or the Institution(s) at which the study is conducted in accordance with a signed clinical trial agreement.

The study sponsor will designate a monitor to conduct the appropriate site visits at the appropriate intervals according to the study monitoring plan. The clinical investigation will be monitored to ensure that the rights and well-being of the subjects are protected, the reported data are accurate, complete, and verifiable from the source documents, and the study is conducted in compliance with the current approved protocol (and amendments[s], if applicable), with current GCP, and with applicable regulatory requirements.

The site may not screen subjects or perform the informed consent process on any subject until it receives a notification from an appropriate Study Sponsor representative that the site may

commence conducting study activities. Monitoring will be conducted periodically while the clinical study is ongoing. Monitoring methods may include site visits, telephone, written and fax correspondence. Close-out visits will take place after the last visit of the last subject at the site.

13.5 Regulatory Documentation and Records Retention

The investigator is required to maintain up-to-date, complete regulatory documentation as indicated by the study sponsor and the investigator's files will be reviewed as part of the ongoing study monitoring. Financial information is to be kept separately.

Additionally, the investigator must keep study records and source documents consistent with the terms of the clinical study agreement with the study sponsor. If the investigator retires, relocates, or for any other reason withdraws from responsibility of keeping the study records, then the study sponsor must be notified and suitable arrangements made for retention of study records and source documents needed to comply with national and international regulations.

13.6 Quality Assurance and Quality Control

The study sponsor will secure agreement from all involved parties to ensure direct access to all study related sites, source data and documents, and reports for the purpose of monitoring and auditing by the study sponsor, and inspection by domestic and foreign regulatory authorities. Quality control will be applied to each stage of data handling to ensure that all data are reliable and have been processed correctly. Agreements made by the study sponsor with the investigator/institution and any other parties involved in the clinical study will be provided in writing as part of the protocol or as a separate agreement.

14 ETHICS

Investigations are conducted in compliance with Good Clinical Practices; international and national regulations, laws, and guidelines; the conditions of approval imposed by reviewing IRBs/IECs or regulatory authorities; and in accordance with the ethical medical research principles outlined in the Declaration of Helsinki.

- The SOPs of the study sponsor and contract research organizations participating in the conduct of the clinical study and all other applicable regulations shall apply.
- Notifications and timelines for reporting protocol deviations should be based upon applicable Ethics Committee requirements.

The investigator must ensure that all personnel involved in the conduct of the study are qualified to perform their assigned responsibilities through relevant education, training, and

experience. The investigator and all clinical study staff must conduct the clinical study in compliance with the protocol. Deviations from this protocol, regulatory requirements, and/or GCP must be recorded and reported to the Sponsor prior to database lock. If needed, corrective and preventive action should be identified, implemented, and documented within the study records. Use of waivers to deviate from the clinical protocol is prohibited.

Before clinical study initiation, this protocol, the informed consent form, any other written information given to subjects, and any advertisements planned for subject recruitment must be approved by an IRB/IEC. The investigator must provide documentation of the IRB/IEC approval to the study sponsor. The approval must be dated and must identify the applicable protocol, amendments (if any), informed consent form, assent form (if any), all applicable recruiting materials, written information for subject, and subject compensation programs. The IRB/IEC must be provided with a copy of the IFU, any periodic safety updates, and all other information as required by local regulation and/or the IRB/IEC. At the end of the study, the investigator must notify the IRB/IEC about the study's completion. The IRB/IEC also must be notified if the study is terminated prematurely. Finally, the investigator must report to the IRB/IEC on the progress of the study at intervals stipulated by the IRB/IEC.

Voluntary informed consent must be obtained in writing from every subject. The obtaining of consent shall be documented before any procedure specific to the clinical investigation is applied to the subject.

The investigator must have a defined process for obtaining the required consent. Specifically, the investigator, or their delegate, must explain the clinical study to each potential subject and the subject must indicate voluntary consent by signing and dating the approved informed consent form. The subject must be provided an opportunity to ask questions of the investigator, and if required by local regulation, other qualified personnel. The investigator must provide the subject with a copy of the consent form written in a language the subject understands. The consent document must meet all applicable local laws and provide subjects with information regarding the purpose, procedures, requirements, and restrictions of the study, along with any known risks and potential benefits associated with the IP and the study, the available compensation, and the established provisions for maintaining confidentiality of personal, protected health information. Subjects will be told about the voluntary nature of participation in the study and must be provided with contact information for the appropriate individuals should questions or concerns arise during the study. The subject also must be told that their records may be accessed by appropriate authorities and sponsor-designated personnel. The investigator must keep the original, signed copy of the consent (file in

subject's medical records) and must provide a duplicate copy to each subject according to local regulations.

Human clinical trials liability insurance will be provided for participating subjects.

The study sponsor assures that the key design elements of this protocol will be registered on www.clinicaltrials.gov if required by current regulations and, if applicable, other public databases as required by local country regulations. In addition, results of this study will be made publicly available on www.clinicaltrials.gov regardless of outcome if required by current regulations and, if applicable, in other public databases as required by local country regulations.

